## 4 Change to protocol specified analyses

Changes to analyses specified in CSP version 03 dated 14-Sep-2023 at the time of SAP amendment 1 finalization on 29-Oct-2024 are as follows (relevant SAP section[s] are indicated in parentheses):

- Changed the primary clinical question of interest in primary estimand section to be focused on NEDA-3 at 18 months ([Section 1.2.1](#))
- Changed the definition of intercurrent event for primary estimand to be treatment discontinuation due to lack of efficacy or death ([Section 1.2.1](#) and [Section 2.5.1](#))
- Updated the definition of the HCAS to remove the requirement for having at least one valid assessment of variables of interest ([Section 2.2](#))
- Defined a new analysis set, the modified FAS (mFAS), to be used for NEDA-3, NEDA clinical and NEDA radiological efficacy analyses ([Section 2.2](#) and [Section 2.6.2](#))
- Defined a new analysis set, the per-protocol set (PPS), to be used for a supplemental efficacy analysis of NEDA-3 ([Section 2.2](#) and [Section 2.5.6](#))
- Changed the handling of intercurrent events for the primary estimand to reflect a composite variable strategy for the handling of treatment discontinuations ([Section 2.5.3](#))

- Changed the handling of missing values not related to intercurrent events for the primary estimand to clarify that, if treatment discontinuation is due to reasons other than lack of efficacy or death, participants who had NEDA-3 before early discontinuations will be excluded from mFAS for all NEDA-3 and associated endpoints efficacy analyses and thusly out of scope for intercurrent events handling (Section 2.5.4)
- Specified supplemental analyses of the primary endpoint (Section 2.5.6):
  - Using an observed case approach (completers) using the FAS
  - Using the PPS
  - Using the mFAS in which the MRI-activity free component of NEDA-3 is defined as no new or enlarging T2 lesions
  - Using the mFAS in which the clinical disability progression-free component of NEDA-3 is based on 6-month clinical disability progression-free
- Clarified that secondary endpoints ‘Number of confirmed relapses’ and ‘3-month disability worsening-free’ are derived in Months 6 to 18 (Section 1.2 and Section 2.6.1)
- Indicated that change and percent change (lesion volume and brain volume parameters) from Month 6 re-baseline to post-Month 6 time points in conventional MRI metrics will be evaluated (Section 2.6.1 and Section 2.6.2); clarified ‘brain volume loss assessment’ as ‘brain volume assessment’ (Section 1.2)

- [REDACTED]
- [REDACTED]

Changes to analyses specified in CSP version 03 dated 14-Sep-2023 at the time of SAP amendment 2 finalization on 22-Apr-2025 are as follows (relevant SAP section[s] are indicated in parentheses):

- [REDACTED]

## **5 Appendix**

### **5.1 Imputation rules**

#### **5.1.1 Study drug**

There will be no imputation rules for study drug detailed for this study.

#### **5.1.2 AE date imputation**

The following algorithm will be used to estimate AE start dates for which only partial information is known. Note that “index date” refers to the date of the first dose of ofatumumab for ofatumumab-treated participants and the date of the Week 0 visit for healthy control participants.

##### **Missing day and month:**

- If the year is the same as the year of the index date, then the day and month of the index date will be assigned to the missing fields.
- If the year is prior to the year of the index date, then December 31 will be assigned to the missing fields.
- If the year is after the year of the index date, then January 1 will be assigned to the missing fields.

##### **Missing month only:**

- Treat day as missing and replace both month and day according to the above procedure.

##### **Missing day only:**

- If the month and year are the same as the year and month of the index date, then the index date will be assigned to the missing day.
- If the month and year are before the year and month of the index date, then the last day of the month will be assigned to the missing day.
- If the month and year are after the year and month of the index date, then the first day of the month will be assigned to the missing day.

If the imputed start date result is after the stop date (and the stop date is complete), the imputed start date will be reset to the stop date.

The following algorithm will be used to estimate AE stop dates for which only partial information is known.

##### **Missing year:**

- Date left missing.

##### **Missing month:**

- Impute ‘December’.

##### **Missing day:**

- Impute ‘last date of that month’.

### 5.1.3 Concomitant medication date imputation

The following algorithm will be used to estimate medication start dates for which only partial information is known. Note that “index date” refers to the date of the first dose of ofatumumab for ofatumumab-treated participants and the date of the Week 0 visit for healthy control participants.

#### Missing day and month:

- If the year is the same as the year of the index date, then the day and month of the index date will be assigned to the missing fields.
- If the year is prior to the year of the index date, then December 31 will be assigned to the missing fields.
- If the year is after the year of the index date, then January 1 will be assigned to the missing fields.

#### Missing month only:

- Treat day as missing and replace both month and day according to the above procedure.

#### Missing day only:

- If the month and year are the same as the year and month of the index date, then the index date will be assigned to the missing day.
- If the month and year are before the year and month of the index date, then the last day of the month will be assigned to the missing day.
- If the month and year are after the year and month of the index date, then the first day of the month will be assigned to the missing day.

If the imputed start date result is after the stop date (and the stop date is complete), the imputed start date will be reset to the stop date.

The following algorithm will be used to estimate medication stop dates for which only partial information is known.

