#### **2.4.2 Prior, concomitant and post therapies**

Medications will be coded using the World Health Organization (WHO) Drug Dictionary. The WHO Drug Dictionary version used for reporting the study will be indicated in a footnote on relevant outputs.

Medications will be classified as prior or concomitant as follows:

- Prior medications are defined as medications taken and stopped prior to the date of the first dose of ofatumumab for ofatumumab-treated participants, or prior to the date of the Week 0 visit for healthy control participants.
- Concomitant medications are defined as medications that started on or after the date of the first dose and within 30 days (inclusive) following the date of the last dose of ofatumumab for ofatumumab-treated participants, or on or after the date of the Week 0 visit for healthy control participants. Note the 30-day window post last dose of ofatumumab is not applicable to ofatumumab-treated participants who are ongoing in the study at the time of the Month 18 interim analysis.
  - For ofatumumab-treated participants, this includes medications that started prior to the date of the first dose and ended on or after the date of the first dose (and within 30 days [inclusive] following the date of the last dose) or are indicated as ongoing.
  - For healthy control participants, this includes medications that started prior to the date of the Week 0 visit and ended on or after the date of the Week 0 visit or are indicated as ongoing.

Medications will be categorized into the above classes based on recorded or imputed start and end dates (see [Section 5.1.3](#)).

Prior and concomitant medications will be summarized with frequency counts and percentages by Cohort, Anatomical Therapeutic Chemical (ATC) class and PT using the SAF or HCAS, as appropriate. Concomitant medications will be summarized for the open-label treatment phase, open-label extension period and overall. Tables will show the overall number and percentage of participants receiving at least one medication of a particular ATC class and at least one medication of a particular PT.

Non-drug therapies/procedures will be coded using MedDRA terminology. The MedDRA version used for reporting the study will be indicated in a footnote on relevant outputs. Non-drug therapies/procedures will be classified as prior or concomitant based on recorded or imputed start and end dates as outlined above for medications.

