### **2.7.1 Adverse events (AEs)**

Adverse events (AEs) will be coded using MedDRA terminology. The MedDRA version used for reporting the study will be indicated in a footnote on relevant outputs.

For reporting purposes, summary tables for AEs will summarize only the following events for ofatumumab-treated participants and healthy control participants:

- On-treatment events (treatment-emergent AEs), which started or worsened on or after the date of the first dose of ofatumumab for ofatumumab-treated participants
- On-study events, which started or worsened on or after the date of the date of Week 0 visit for healthy control participants

The number and percentage of participants with treatment-emergent/on-study AEs will be summarized for the open-label treatment phase, open-label extension period and overall, in the following ways using the SAF or HCAS, as appropriate:

- by Cohort, primary SOC and PT
- by Cohort, primary SOC, PT and maximum severity
- by Cohort and PT

Separate summaries will be provided using the SAF or HCAS, as appropriate, for treatment-emergent/on-study AEs occurring with a frequency of >5% in either Cohort, treatment-related AEs (only applicable to ofatumumab-treated participants), AEs leading to study drug interruptions (only applicable to ofatumumab-treated participants), serious adverse events (SAEs), treatment-related SAEs (only applicable to ofatumumab-treated participants) and other significant AEs leading to discontinuation.

In addition, an overview of treatment-emergent/on-study AEs will be summarized for the open-label treatment phase, open-label extension period and overall, presenting the number and percentage of participants having at least one AE for each of the categories described above.

If a participant reported more than one AE with the same PT, the AE with the greatest severity will be presented. A participant with multiple AEs within a primary SOC is only counted once towards the total of the primary SOC.

Partial AE start and end dates will be imputed as outlined in [Section 5.1.2](#).

For the legal requirements of ClinicalTrials.gov and EudraCT, two required tables on on-treatment/treatment-emergent AEs which are not SAEs with an incidence greater than 5% and

on on-treatment/treatment-emergent SAEs and SAEs suspected to be related to study treatment will be provided by SOC and PT on the SAF.

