#### Missing day:

- Impute ‘last date of that month’.

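### In one pattern of partial dates, SAP 5.1.2 and 5.1.3 start a record at the first dose although its stop month shows that it ended earlier

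*SAP*

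**What the plan says.** The same algorithm stands in SAP 5.1.2 for AEs and in SAP 5.1.3 for medications. SAP 5.1.3.1 and 5.1.3.2 extend it to prior and post therapies. The index date is the first dose for ofatumumab participants and the Week 0 visit for healthy controls.

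- **Start, day and month missing, year equal to the index year:** "then the day and month of the index date will be assigned to the missing fields". A start missing only its month is treated the same way.
- **Reset:** if the imputed start falls "after the stop date (and the stop date is complete), the imputed start date will be reset to the stop date".
- **Stop, day missing:** imputed as "last date of that month". This rule comes after the reset, and no later step compares the two dates.

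Two sections then use these dates:

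- **SAP 2.4.2** calls a medication prior if it was stopped before the first dose. It also says "Concomitant medications are defined as medications that started on or after the date of the first dose" (and within 30 days of the last dose). Both classes rest on recorded or imputed dates, and no order of precedence is given. Non-drug therapies follow the same scheme.
- **SAP 2.7.1** counts as treatment-emergent those events "which started or worsened on or after the date of the first dose of ofatumumab for ofatumumab-treated participants". The stop date plays no part. The rule for healthy controls is the same, counted from Week 0.

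**The concern.** The reset exists to prevent a default start date from contradicting a known end date. Limiting it to complete stop dates leaves out a case in which the stop is still informative. A stop known to the month, in a month before the index month, already shows that the drug or event ended before the index date. The start rule nevertheless places it on that date.

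What is at stake is the content of descriptive safety and medication tables. A screening event may be counted as treatment-emergent, and a drug finished before entry may appear among those taken on ofatumumab.

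**Working it through.** The plan states no figure to reproduce here, so the check applies the date rules as written.

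**Medication example** (the dates are illustrative assumptions). First dose 15-Jun-2022, start recorded as 2022, stop recorded as Mar-2022.

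1. The start lacks its month and its year is the index year, so start = 15-Jun-2022.
2. The recorded stop is not complete, so there is no reset.
3. The stop lacks its day, so stop = 31-Mar-2022.
4. Start minus stop = 30 (April) + 31 (May) + 15 (June) = 76 days, so the record begins 76 days after it ends.
5. Under SAP 2.4.2, the stop before 15-Jun makes it prior, and the start on 15-Jun makes it concomitant.

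**AE example.** AEs are recorded from consent (Protocol 10.1.1) and screening lasts up to 4 weeks (SAP 1.1). With first dose 15-Jun-2022, screening starts no earlier than 18-May-2022. Start 2022 and stop May-2022 give start 15-Jun-2022 and stop 31-May-2022, a gap of 15 days. SAP 2.7.1 looks only at the start, so the event is treatment-emergent.

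**All nine combinations of precision**, for records whose recorded or imputed stop lies before first dose:

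| Start known to | Stop: full date | Stop: month and year | Stop: year only |
|---|---|---|---|
| Full date | correct | correct | correct |
| Month and year | correct | correct | correct |
| Year (month missing) | correct, reset applies | **fails if start and stop are both in the index year** | correct |

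- A start missing only its day cannot fall in the index month if the stop month is earlier.
- A year-only stop becomes 31 December, so it precedes first dose only if it lies in an earlier year. The start then lies in an earlier year too.
- With a month-and-year stop and a year-only start in an earlier year, the dates can still be out of order: start 2021 and stop Jun-2021 give 31-Dec-2021 and 30-Jun-2021. Both precede first dose, so the class is right.

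**Enumeration.** The rules were run on a 3-day grid of true start and stop dates, going back to 1 January of the year before first dose. The table counts date pairs in the failing cell (month-missing start, month-and-year stop).

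| First dose (assumed) | Pairs in cell | Misclassified as written | Misclassified with reset on imputed stops |
|---|---|---|---|
| 10-Jan-2022 | 7,503 | 0 | 0 |
| 15-Jun-2022 | 14,878 | 1,275 | 0 |
| 20-Dec-2022 | 27,261 | 6,216 | 0 |

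No other cell produced a misclassification. With first dose in January there is no earlier month in the year, so the case cannot arise. These are counts of possible calendar dates, not of trial records, and say nothing about how often the pattern will occur.

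**The case against.** The strongest reply is that few such records will reach the analysis.

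- Protocol 11.1 and 11.2 provide automatic checks and queries for discrepancies and missing values before lock. A year-only start in the enrolment year is an obvious query.
- A failing AE must begin and end within about four weeks, in a calendar month before the first-dose month of the same year. Its stop month must be known while its start month is not.
- The outputs are descriptive, and SAP 5.4 plans no hypothesis test.

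All of this stands and limits the size. None of it corrects the rule for the records that remain, and imputation rules exist for those records.

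A second reply is that a complete stop date might include an imputed one, in which case the problem disappears. The text does not favour this: the reset comes before stop imputation, and a month-end default was not complete as recorded. If it is what was meant, the SAP needs to say so.

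A reader might also infer that on-study deviations or relapse treatments would be falsely suggested, for example by steroids given for the presenting relapse. The documents do not support that:

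- Protocol 6.2.3 requires at least 30 days from the last steroid or plasmapheresis treatment to the screening MRI, so sites need close timing of that stop.
- No SAP rule derives deviations or relapses from imputed medication dates.
- Relapse records carry their own corticosteroid item (SAP 5.1.3.4), and relapse dates have separate imputation rules (SAP 5.1.3.3).

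**Conclusion.** The point holds for one date pattern: a start without its month in the index year, and a stop known only to a month and year in an earlier month of that same year. An AE with these dates is wrongly counted as treatment-emergent, or on-study for a healthy control. A medication or non-drug therapy falls into both classes, or its class is left to the programmer.

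Two broader readings are tempting. One is that any drug or event known to have ended before first dose is misdated; the other eight combinations show otherwise. The other is that affected medications are listed only as concomitant; they also meet the prior definition.

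The number of affected records cannot be derived from the documents. It is probably small and mainly medications. NEDA-3 does not use these dates. The conclusion assumes that a complete stop date means complete as recorded.

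**What to change.** In both SAP 5.1.2 and 5.1.3, place stop-date imputation before the reset, delete the parenthetical condition on a complete stop date, and state: *If the imputed start date is after the recorded or imputed stop date, the start date is set to the stop date.*

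In the examples the medication start becomes 31-Mar-2022, so the record is prior only. The AE start becomes 31-May-2022, so the event is not treatment-emergent. The sentence also puts the earlier-year dates in order without changing their class.

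The cost is one sentence in two sections and a small programming change. It needs no new data and leaves the primary analysis unchanged.

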#### Missing year:

- Date left missing.

#### Missing month:

- Impute ‘December’.

#### Missing day:

- Impute ‘last date of that month’.

#### 5.1.3.1 Prior therapies date imputation

Same as for medications above.

#### 5.1.3.2 Post therapies date imputation

Same as for medications above.

### 5.1.3.3 Other imputations

#### Non-response imputation

NRI assumes that a participant is a non-responder (treatment failure) if the participant does not have a complete set of valid response assessments (relapse, disability [EDSS] and MRI) in Months 6 to 18 after receiving at least one dose of ofatumumab. Hence, for missing data the primary endpoint of NEDA-3 in Months 6 to 18 (yes/no) will be imputed as “No”.

#### MS relapse date imputation

Missing or partial MS relapse start and end dates are not expected.

The following algorithm will be used to estimate MS relapse start dates for which only partial information is known (i.e., month and year are available but day is missing). Note that “index date” refers to the date of the first dose of ofatumumab.

##### Missing day only:

- The first day of the month will be assigned to the missing day. In case the relapse start date occurs in the same month as the index date, the relapse start date will be imputed as the index date.

The following algorithm will be used to estimate MS relapse stop dates for which only partial information is known (i.e., month and year are available but day is missing). Note that “index date” refers to the date of the first dose of ofatumumab.

##### Missing day only:

- The last day of the month will be assigned to the missing day or truncated to have a maximum duration of 90 days.

#### MS history date imputation

For the derivation of “time from onset of most recent relapse to first dose of ofatumumab”, “time from RRMS diagnosis to first dose of ofatumumab” and “time from first MS symptoms to first dose of ofatumumab” (see [Section 2.3.3](#)), the following algorithm will be used to estimate most recent relapse onset dates, RRMS diagnosis dates and first MS symptoms dates for which only partial information is known.

##### Year is missing or impossible (e.g., 12-Jan-1911):

- Date will be imputed as missing.

##### Missing day and month:

- July 1 will be assigned to the missing day and month.

##### Missing day only:

- The 15th of the month will be assigned to the missing day.

The imputed date should be prior to the date of the Screening visit. However, if the imputed date is on or after the date of the Screening visit, it will be reset to be one day prior to the Screening visit date.

#### **5.1.3.4 Data handling for relapses within 30 days of onset of previous relapses or relapses with duration beyond 90 days**

According to protocol definition of MS relapses, the start date of a new relapse has to be at least 30 days after the start date of a previous relapse (i.e., start date of a new relapse – start date of a previous relapse  $\geq 30$ ). If a relapse is recorded with a start date less than 30 days after the start date of a previous relapse, the below data manipulation will be done to combine them into a single relapse by creating a new relapse record with the following information.

- Start date: take the earliest start date.
- End date: take the latest end date. If one of the end dates is missing, set it to missing.
- Date of EDSS intended to confirm the relapse:
  - Take the date of EDSS by which the relapse can be confirmed.
  - If more than one EDSS assessment meets the above criteria, take the date of EDSS by which the worst severity value is derived.
  - If no EDSS assessment meets the above criteria, take the earliest date of EDSS as captured on the relapse CRF page.
- “Affects daily activities?”, “Was the participant hospitalized for this MS relapse?”, “Was corticosteroid treatment taken for this MS relapse?”, “Recovery from MS relapse”: for each of these characteristics, take the value representing the worst case (i.e., yes > no for first 3 questions; no > partial > complete recovery for last question).

The maximum duration of a relapse is 90 days. If a relapse is recorded with a duration longer than 90 days, the end date will be truncated to have a duration of exactly 90 days. This applies also to the artificial record created by the above procedure. A missing end date of relapse is not allowed. In the rare case that a missing end date exists in the final database, it will be imputed so that the duration of relapse is exactly 90 days.

## **5.2 AEs coding/grading**

Adverse events will be coded using the MedDRA terminology. The MedDRA version used for reporting the study will be indicated in a footnote on relevant outputs.

## **5.3 Laboratory parameters derivations**

The following derivations will be performed for continuous laboratory variables:

- If variables are databased as <lower limit, these will be imputed as being half of the lower limit. For example, Brain-Derived Neurotrophic Factor with a value of <.013000000 will be imputed to be 0.0065.
- If variables are databased as >upper limit, these values will be excluded from the analysis.

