			13. Removed analysis using the per-protocol set	16. Section 2.6.2 Statistical hypothesis, model, and method of analysis
			14. Removed analysis of percent change from baseline and Month 6 re-baseline in lesion volume parameters	17. Section 2.7.1 Adverse events (AEs)
			15. Clarified determination of number of new/enlarging T2 lesions for derivation of annualized new/enlarging T2 lesion rate	18. Section 2.7.1 Adverse events (AEs)
			16. Removed observed case approach for summarization of participants with confirmed relapses	19. Section 2.7.1.1 Adverse events of special interest / grouping of AEs
			17. Added summaries for treatment-related SAEs and AEs occurring with frequency >5%	20. Section 2.10 Patient-reported outcomes
			18. Added details regarding summarization of AEs needed for ClinicalTrials.gov and EudraCT	21. [REDACTED]
			19. Removed summary of infection-related AEs	22. [REDACTED]
			20. Clarified that only total raw score for NeuroQOL Communication short form domain will be summarized	23. [REDACTED]
			21. Indicated that analysis of NfL values will not occur for the Month 18 interim analysis; NfL values will be analyzed at the time of the final analysis for the study	24. [REDACTED]
			22. [REDACTED]	25. Section 4 Change to protocol specified analyses
				26. Section 5.1.3.3 Other imputations
				27. Section 5.1.3.4 Data handling for relapses within 30 days of onset of previous relapses or relapses with duration beyond 90 days
				28. Section 5.3 Laboratory parameters derivations
				29. Section 5.5 Rule of exclusion criteria of analysis sets
				30. Section 6 Reference

---

Date	Time point	Reason for update	Outcome for update	Section and title impacted (Current)
			23. Removed analysis of [REDACTED] adverse events over the course of the study	
			24. Updated derivations for PDC and MPR	
			25. Indicted removal of analysis of [REDACTED] adverse events over the course of the study	
			26. Clarified MS history date imputation rules	
			27. Removed severity determination of "linked" relapses	
			28. Added rules for conversion of character to numeric continuous laboratory values	
			29. Removed reference to per-protocol set	
			30. Added Brookmeyer and Crowley reference	

---

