### **2.7.3 Laboratory data**

Shift tables using the low/normal/high/ (low and high) classification will be used to compare baseline to the worst on-treatment value for hematology and chemistry parameters using the SAF. In particular, the number and percentage of participants with laboratory values will be presented by low/normal/high/ (low and high) classifications to compare baseline to worst on-treatment value for the open-label treatment phase, open-label extension period and overall. Unscheduled assessments will be considered.

Values and changes from baseline in hematology and chemistry parameters will be summarized by time point with descriptive statistics using the SAF.

Laboratory abnormalities will be flagged in listings.

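### SAP 5.3 excludes laboratory results reported as above the upper limit but keeps those below the lower limit; this lowers by-visit means and, as written, would drop known high results from the shift tables

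*SAP*

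**What the plan says.** SAP 5.3 opens with a general scope: "The following derivations will be performed for continuous laboratory variables". Two rules follow. For the low end: "If variables are databased as <lower limit, these will be imputed as being half of the lower limit". For the high end: "If variables are databased as >upper limit, these values will be excluded from the analysis". The one worked example is at the low end: "Brain-Derived Neurotrophic Factor with a value of <.013000000 will be imputed to be 0.0065". The SAP document history describes the addition, made in Amendment 2, as "Added rules for conversion of character to numeric continuous laboratory values".

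SAP 2.7.3 plans two summaries of these data. Shift tables by low/normal/high class are used to "compare baseline to the worst on-treatment value for hematology and chemistry parameters using the SAF", with unscheduled assessments considered. The second summary is by visit: "Values and changes from baseline in hematology and chemistry parameters will be summarized by time point with descriptive statistics using the SAF". Section 2.7.3 also has abnormalities flagged in listings. It does not say how a result above the upper limit enters either summary.

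**The concern.** The limit is best read as an assay reporting limit, not the upper end of the reference range. The worked example is an assay-type value, and the history entry concerns turning character results into numbers. On that reading a result above the limit carries real information: it is larger than any value the assay reports as a number. The plan keeps the equivalent result at the low end and discards this one.

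Two outputs are at stake. By-visit means lose their largest contributors. The shift table, whose purpose is to show each participant's worst value, could lose the results it most needs. The chemistry panel in Protocol Table 8-4 includes ALT, AST, GGT, bilirubin, amylase, lipase and creatinine, where high values are the safety question.

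**Working it through.** **The plan's own figure.** 0.013 / 2 = 0.0065, which matches the example in SAP 5.3.

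**Inputs.** The rule is from SAP 5.3 and the summaries from SAP 2.7.3. The laboratory visit windows are from SAP Table 5. The planned number of treated participants, 118, is from SAP 3.1. The share q of results above the upper limit is not in the documents. It is assumed here to be 1% to 10% for means and 1% to 2% for shift tables.

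**By-visit means, direction.** With a common limit for the assay, every excluded value exceeds every retained one. Removing any of them must lower the mean. No assumption about q is needed.

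**By-visit means, size.** For a standard normal variable let c be the point with share q above it and φ the normal density.

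- Excluded: mean = -φ(c) / (1 - q)
- Set to the limit: mean = -φ(c) + q × c

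At q = 5%, c = 1.645 and φ(c) = 0.1031. Exclusion gives -0.1031 / 0.95 = -0.109. Setting to the limit gives -0.1031 + 0.0822 = -0.021.

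For a lognormal variable with log-SD s and Φ the normal distribution function, the ratio to the true mean is Φ(c - s) / (1 - q) when values are excluded, and Φ(c - s) + q × exp(s × c - s²/2) when they are set to the limit.

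| Assumed q | Values lost of 118 | Normal, excluded (SD) | Normal, set to limit (SD) | Log-SD 0.5, excluded / set | Log-SD 1.0, excluded / set |
|---|---|---|---|---|---|
| 1% | 1.2 | -0.027 | -0.003 | -2.4% / -0.6% | -8.3% / -3.0% |
| 2% | 2.4 | -0.049 | -0.007 | -4.1% / -1.1% | -12.9% / -5.1% |
| 5% | 5.9 | -0.109 | -0.021 | -8.0% / -2.6% | -22.1% / -10.2% |
| 10% | 11.8 | -0.195 | -0.047 | -13.0% / -5.0% | -32.1% / -17.1% |

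**Change from baseline.** SAP 2.1.1 calculates change only where both values exist. An excluded high post-baseline value tends to remove a rise, which pulls the mean change down. An excluded high baseline tends to remove a fall, which pushes it up. The net direction cannot be determined.

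**Shift table, if the rule is applied to it.** Let h be the true share High. After exclusion the table shows (h - q) / (1 - q).

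- h = 5%, q = 1%: 0.04 / 0.99 = 4.0%
- h = 5%, q = 2%: 0.03 / 0.98 = 3.1%
- h = 3%, q = 1%: 0.02 / 0.99 = 2.0%
- h = 3%, q = 2%: 0.01 / 0.98 = 1.0%

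SAP Table 5 has windows only for Baseline, Month 18 and Month 30, so one on-treatment sample is scheduled before the Month 18 cut-off. If that result is above the limit, the participant has no worst value for the phase unless an unscheduled sample exists. If one does, the participant is classified by a less extreme value.

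**The case against.** The strongest case on the other side is that the practical effect may be very small. Nothing in the documents suggests that results above an assay limit are common in hematology and chemistry for adults aged 18 to 35. At q = 1% about one value in 118 is lost and the normal mean moves 0.027 SD, while the standard error of a mean at n = 118 is 1/√118 = 0.092 SD. That is about a third of a standard error. Medians and quartiles are reported too, and there is no hypothesis testing. All of this stands and limits the weight of the point. It does not justify the rule, because rare extreme results are what a worst-value table is meant to show, and they can be classed without knowing their exact size.

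A second objection is that the shift table is categorical, whereas SAP 5.3 speaks of continuous variables. The classes might come from a laboratory range flag and so bypass the exclusion. No section says so, and none says the opposite. Loss from the shift table is the natural reading of 5.3 with 2.7.3, not an explicit statement.

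Two stronger readings are tempting, and the documents do not support them.

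- A reader might infer that changes from baseline are also biased downward. They need not be, because the rule excludes high baselines as well.
- A reader might infer that the largest abnormalities disappear from safety reporting. They do not. SAP 2.7.3 flags abnormalities in listings. Protocol 8.4.1 requires clinically significant ones to be recorded as medical history or adverse events. SAP 2.7.1 summarizes treatment-emergent adverse events, including by maximum severity.

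The effect on biomarkers cannot be judged fully either. The example shows that the rule reaches at least one, but much of the related SAP text is redacted.

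**Conclusion.** The point holds for the laboratory summary tables. The asymmetry is explicit, and the downward bias of by-visit means follows whenever a result above the limit occurs. Its size rests on an assumed share: -0.03 to -0.20 SD for normal data at 1% to 10%, and more in relative terms for skewed data. The lower end is the more plausible for routine laboratory tests. As written, the rule would also take these results out of the worst-value shift tables, subject to the ambiguity over how the classes are derived. The loss is from the laboratory summaries and not from the record. NEDA-3 and the sample size are unaffected. This should be corrected because it concerns safety output and costs little, but it does not threaten the trial's main conclusion.

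**What to change.** In SAP 5.3, replace the exclusion with a rule that sets results above the upper limit to the upper limit for descriptive statistics, with a table footnote giving their number by parameter and time point. State in 5.3 and 2.7.3 that these results are retained in the shift tables and classified against the reference range, which makes them High wherever the assay limit lies at or above the upper reference limit.

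The cost is a sentence or two in each section and a footnote in the table shells, with no new data. Capping is not unbiased. It leaves -0.003 to -0.05 SD for normal data over the same assumed range, and more for strongly skewed data, which is why the footnote is needed. It does leave the median and quartiles unchanged as long as fewer than a quarter of values lie above the limit.
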